11. SAFETY AND TOLERABILITY ANALYSES

All safety end points will be presented by using the safety population.

11.1 Adverse Events

An overall summary of AEs will be presented and will include the number and percentages of subjects with

- any adverse events
- catheter-related adverse events
- procedure related adverse events
- study drug related adverse events
- primary adverse events
- serious adverse events
- adverse events leading to withdrawal

All adverse events will be coded using MedDRA coding dictionary.

Summaries of incidence rates of individual AE (number and percentage of subjects) by MedDRA system organ class and preferred term will be prepared.

Such summaries will be displayed for all AE, AE by maximum severity and AE by strongest causality to catheter, procedure or study drugs.

In these summaries, each subject will be counted only once within each category. If a subject experiences more than one AE within a category, only the AE with the strongest causality or the maximum severity, as appropriate, will be included in the summaries by causality and severity.

11.2 Catheter-related complications (AEs)

A key secondary safety endpoint, catheter-related complications (AEs), is limited to subjects who have initiated RF ablation and who are in the safety population. Catheter-related AEs are those AEs that are identified as possibly, probably or definitely related to the study device. The number and percentage of subjects with catheter-related AEs will be summarized by system organ class and preferred term for Test Group and cross-over subjects and overall in the safety population. Moreover, catheter-related complications will be summarized (overall, all types accumulated), in a further table containing the number and percentage of subjects with catheter-related complications by number of repeat ablations, by anticipated or not, by severity and by outcome.

11.3 Serious AEs

The number and percentage of subjects with SAEs will be summarized by system organ class and preferred term for both treatment groups and overall and in a further table by causality and by severity.

The summary by AE category will also be prepared for serious catheter-related AEs and serious catheter-related AEs by timeframe. Three timeframes will be included in this summary: acute phase AEs (ablation to ≤ 7 days) and sub-chronic AEs (>7 to 30 days post ablation), and chronic AEs (occurring more than 30 days post ablation).

11.4 Primary AEs

Primary AEs are defined as specific AEs that occur within 7 days of ablation procedure (AE categories as defined in the study protocol).

The number and percentage of subjects with primary AEs will be summarized by system organ class and preferred term, overall and by treatment group.

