##### **Primary Adverse Event (AE):**

A primary AE includes any of the following outcomes that occur within 7 days of an AF ablation procedure :

- Death
- Myocardial infarction (MI)
- Pulmonary vein (PV) stenosis\*
- Diaphragmatic paralysis
- Atrio-esophageal fistula\*
- Transient Ischemic Attack (TIA)
- Stroke / Cerebrovascular accident (CVA)
- Thromboembolism
- Bleeding (including haematoma) requiring blood transfusion
- Pericarditis
- Cardiac Tamponade
- Pericardial effusion
- Pneumothorax
- A study perforation
- Vascular Access Complications
- Pulmonary edema
- Hospitalization (initial and prolonged)†
- Heart block

\* Pulmonary vein stenosis and atrio-esophageal fistula that occurs greater than one week (7 days) post-procedure shall be deemed a primary AE.

† Excludes hospitalization solely due to pre-existing arrhythmia recurrence.

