Thrombus formation on the endocardium following ablation may produce an arterial or pulmonary embolus. This risk may be reduced by the use of aspirin (antithrombotic) and/or anticoagulation therapy, at the discretion of the investigator.

Cardiac perforation may result from catheter manipulation or application of radiofrequency current (risk is <1%). This may result in cardiac tamponade and may require percutaneous pericardial drainage or surgical repair. Significant hemodynamic compromise can result in neurologic injury or death. An increased risk of cardiac perforation may be associated with the use of a saline-irrigated electrode catheter due to its ability to create a larger, deeper RF lesion. This risk is greatest in a thin walled chamber (i.e., RA, LA, or RV); however, the risk of perforation related to a deep steam pop is reduced if RF energy is not delivered perpendicular to the wall at power above 35 or 40 watts. If the lesion is deeper, the risk of steam pop is higher above 35-40 watts.

Injury to a cardiac valve may result from catheter manipulation or the application of radiofrequency current (risk <1%). This may produce valvular insufficiency and possibly necessitate valve replacement surgery.

The application of RF current along the posterior left atrium can result in thermal injury to the esophagus and the formation of an atrio-esophageal fistula. This is a very rare (0.04%) but severe complication of RF ablation that may require surgical intervention or result in permanent impairment. Reducing power at sites in close proximity to and/or avoiding sites directly over the esophagus may reduce the risk of thermal injury.

Injury to the phrenic nerve may occur as a result of RF application in the region of the right pulmonary veins. The reported incidence of phrenic nerve injury varies from 0% to 0.48% when RF energy is used for catheter ablation. Prior to ablation in the region of the RSPV, investigators are encouraged to perform precautionary measures, such as evaluation of proximity to the phrenic nerve and pacing maneuvers.

Radiation exposure during fluoroscopic imaging of catheters may result in an increase in the lifetime risk of developing a fatal malignancy (0.1%) or a genetic defect in offspring (0.002%).

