5. CHANGES TO PLANNED ANALYSIS

5.1 Changes for the final analysis

As the study was terminated early, without having met primary effectiveness or futility criteria at the most recent interim analysis, it is not fully obvious which alpha level to use for the primary efficacy analysis. However as the number and time points of the interim analyses had not been fixed in advance, it was decided to spend all alpha remaining for the final analysis, in other words to spend what is left from the total alpha. Moreover, after further discussion, it has been decided to update the calculation of the primary endpoint to use procedure date as start date for time to event calculation rather than randomization date (see section 8.3).

It also was decided to delete some of the analyses originally planned in the protocol:

- For secondary endpoint “factors associated with AF disease progression”, only the main analyses will be performed, and some of the supporting models were deleted
- Analysis of site heterogeneity will not be performed

Moreover, a sensitivity analysis for the primary endpoint and first secondary endpoint was added, using an alternative definition for the primary endpoint based on the consensus statement of the HRS (Heart Rhythm Society, 2017).

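### SAP 11.4 sets a flat 7-day window for primary AEs and omits the protocol's exception for late pulmonary vein stenosis and atrio-esophageal fistula

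*SAP*

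**What the plan says.** Protocol 12.1.1, under the heading for primary adverse events, opens with the general rule: "A primary AE includes any of the following outcomes that occur within 7 days of an AF ablation procedure". Eighteen outcomes follow. Two of them, pulmonary vein stenosis and atrio-esophageal fistula, carry an asterisk, and the note to it reads: "Pulmonary vein stenosis and atrio-esophageal fistula that occurs greater than one week (7 days) post-procedure shall be deemed a primary AE".

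SAP 11.4 gives its own definition: "Primary AEs are defined as specific AEs that occur within 7 days of ablation procedure (AE categories as defined in the study protocol"). It then specifies the output: "The number and percentage of subjects with primary AEs will be summarized by system organ class and preferred term, overall and by treatment group". The planned tables are 14.3.6.1 (by system organ class and preferred term) and 14.3.6.2 (listing of cases, also marked as interim output 3.4). SAP 11.1 uses the same category once more, listing "primary adverse events" as one line of the overall AE summary.

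SAP section 5 records departures from the protocol, including deletions ("It also was decided to delete some of the analyses originally planned in the protocol"). Neither 5.1 nor 5.2 mentions the primary-AE definition.

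**The concern.** The SAP refers to the protocol for which events count but sets the timing itself, with no exception. The protocol deliberately exempted two complications from that timing limit. A program that follows the SAP literally would apply day 7 to all eighteen categories and give a primary-AE count that does not match the protocol's definition of the term. Anyone reading the table with the protocol in hand would take it to include late stenosis and fistula, and it would not. These are rare complications, so a single case can change a line of the table.

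**Working it through.** The point depends on no power, alpha or event calculation. The check is a comparison of the two definitions, followed by a search for anything in the SAP that closes the gap.

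**1. The two rules applied to the same event**

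| Event | Protocol 12.1.1 | SAP 11.4 as written |
|---|---|---|
| Any listed outcome, day 0 to 7 | Primary AE | Primary AE |
| Stenosis or fistula, day 8 or later | Primary AE | Not a primary AE |
| Any other listed outcome, day 8 or later | Not a primary AE | Not a primary AE |

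The rules differ only in the middle row.

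**2. Is the difference declared or repaired elsewhere?** It is not among the changes in SAP 5.1 or 5.2. SAP 11.1 to 11.3, 11.5 and the table list in 15.1 contain no wording that restores the exception. The SAP does flag some departures in its running text, such as the change of population for health economics and quality of life in 8.1, but not this one.

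**3. Would late cases be collected?** Yes. Protocol 12.6.2 has AEs recorded from consent to the end of the study. The gap is in classification, not in the data.

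**4. Where would a late case still be seen?**
- Table 14.3.2 (all AEs) and listing 16.2.23 (interim output 3.2): always, for subjects in the populations shown.
- Tables 14.3.5.1 and 14.3.5.5 (SAEs; the latter is interim output 3.3): if serious.
- Tables 14.3.4.1 and 14.3.4.3 (catheter-related AEs): if judged related to the study device, which is how SAP 11.2 defines catheter-related.
- Table 14.3.5.4 (serious catheter-related AEs by timeframe): if both serious and device-related. SAP 11.3 adds a third window here, "chronic AEs (occurring more than 30 days post ablation"), which Protocol 13.13 did not have.

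None of these reproduces the primary-AE count. The protocol's definition requires neither seriousness nor device causality, and Protocol Table 2 rates device and procedure causality separately. A late stenosis judged non-serious, or related to the procedure but not the device, would miss Table 14.3.5.4.

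**5. Size.** The number of reclassified cases would be (subjects ablated) × (rate of the event) × (share occurring after day 7). The documents do not give the third factor. For the first they give only planning figures: 161 Test subjects plus 50% cross-over from 161 Control subjects, 161 + 0.5 × 161 = 241.5. SAP 5.1 reports that the study ended early, so the actual number may differ. For fistula, Protocol Appendix A says: "This is a very rare (0.04%) but severe complication of RF ablation". On the planning figures that is 241.5 × 0.0004 ≈ 0.1 expected case, early and late together. For stenosis, Appendix A gives only a pooled figure of under 4% for several pulmonary events, which cannot be split by type or by timing.

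**The case against.** The strongest reply is that SAP 11.4 is a short pointer to the protocol, not a self-contained definition. A programmer who takes the categories from Protocol 12.1.1 will see the asterisk on these two entries and find the note, and SAP section 1 tells the reader to consult the protocol. The documents also do not show how the primary-AE flag is derived. It follows that the loss of cases is a consequence of the literal text, not a certainty. The reply does not remove the conflict: the reference covers categories, while the sentence fixes the timing, and a plan should not rely on a footnote elsewhere to override its own stated rule.

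The second reply is that little depends on it. Primary AEs are not among the safety endpoints in Protocol 10.2 or SAP 2.2.2, which are catheter-related complications and adverse drug reactions. Protocol section 13 plans no primary-AE analysis, and no test, threshold or stopping rule uses the count. The catheter-related endpoint in SAP 11.2 has no 7-day limit. All of this stands, and it limits how much the point matters.

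A reader might infer that late stenosis and fistula would drop out of the safety report, or that the protocol ranks these two above the other listed complications. The documents support neither. Step 4 shows where late cases remain visible, and Appendix A calls fistula severe but very rare and the pulmonary risk small, without ranking them above death, stroke or tamponade on the same list.

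**Conclusion.** The SAP definition is wrong as written: it contradicts Protocol 12.1.1 for one defined class of events and does not declare the change. The consequence is limited to Table 14.3.6.1, Table 14.3.6.2 and the primary-AE line of the overall AE summary. Because Table 14.3.6.2 is also an interim output, the same rule could have affected interim listings. SAP 8.3 says those analyses used SAP version 1.0, whose wording on this point is not shown.

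The number of cases affected cannot be computed. It may be zero, and any estimate of one or two missing stenosis cases would need a late-stenosis rate that the documents do not contain. The primary endpoint, alpha and sample size are unaffected. The conclusion assumes that the outputs follow the SAP sentence literally. If the programs already apply the protocol's note, only the text needs correcting.

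**What to change.** Amend the definition in SAP 11.4 to read: *occurring within 7 days of an ablation procedure, and pulmonary vein stenosis or atrio-esophageal fistula at any time after the procedure, per Protocol 12.1.1*. Apply it to Tables 14.3.6.1 and 14.3.6.2 and to the primary-AE line of the overall AE summary. If the narrower window was intended, keep it, but declare and justify it in SAP section 5 and footnote the tables to say that they depart from the protocol's definition.

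The cost is one sentence and one program condition. The AE data are already collected, and no other analysis changes.

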11.5 Adverse Drug Reactions

The number and percentage of subjects with adverse drug reactions defined as AE possibly, probably or definitely related to AAD will be summarized by system organ class and preferred term according to Test Group, cross-over group and Control Group (without cross-over subjects). The number and percentage of subjects with adverse drug reactions will also be summarized by causality, by anticipated or not, by severity and by outcome.

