#### **13.13 Secondary Safety Endpoints Analysis**

A key secondary safety endpoint, catheter-related complications (AEs), is limited to subjects who have initiated RF ablation and who are in the safety population. The number and percentage of catheter-related AEs will be summarized and listed overall by Test Group and cross-over patients in the SP and by number of repeat ablations. The number and percentage of catheter-related complications will also be summarized and listed by AE category, causality, anticipated or not, severity and outcome.

Serious catheter-related AEs will be reported by 2 timeframes: acute phase AEs, ablation to  $\leq 7$  days; and, sub-chronic AEs occurring  $>7$  to 30 days post ablation. Serious AEs will be evaluated by causality and severity, using descriptive statistics.

The number and percentage of adverse drug reactions will be summarized and listed overall, according to Test Group; cross-over; and, Control Group excluding cross-over patients. The number and percentage of adverse drug reactions will also be summarized and listed by drug category and AE category, causality, anticipated or not, severity and outcome.

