## Appendix B: Guidelines and Restrictions for the ATTEST Protocol Regarding Cross-over from the Drug (Control) Group

1. Guidelines and principles for cross-over are to be followed by the investigator as laid down in this document and in the protocol.
2. It is the intent of the Sponsor and organizers of this study that cross-over be significantly reduced from published rates quoted in previous drug versus ablation trials.
3. The crossing over from the drug group undermines the tenets of equipoise that are intended in: (a) the study's collective inclusion/exclusion criteria for all subjects; (b) the eligibility of all subjects at study onset to be randomized to either treatment group; and, (c) the intended balance of AF severity, drug history, concurrent illnesses (HATCH score severity), demographics, and other characteristics, such that legitimate statements might be made in comparing the outcomes of medical management versus ablation therapy. The nature and conditions for cross-over from the Control (AAD therapy) Group to the Test (PVI) Group, in a randomized controlled study, are not well understood and are multi-factorial. Thus, any assumptions that subjects crossing over reflect the general demographics, disease severity, and extent of disease progression within either study group at randomization cannot be held with certainty.
4. One could justifiably argue that those most likely to suffer severe side effect reactions from AAD therapy might be those who take their drugs sporadically, take drugs sometimes too close together (shortened inter-dose time interval), suffer rebound effects from resumption of drugs after a drug holiday, and who do not heed the warnings of physicians/pharmacists about mixing drugs for AF/AT with those for other chronic diseases. One might further argue that those with heightened disease progression, as noted in published literature, would be among the oldest in their randomized study group and that their baseline HATCH scores are likely to be high as well, which is consistent with elderly patients. If one or more of these assumptions are true, those most likely to seek cross-over from the drug group would be among the aforementioned, resulting in a relatively younger, healthier, and more compliant group of subjects remaining in the drug group over the whole 3 year study period. In this context, extensive cross-over certainly would erode equipoise.

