5. The recognized reasons for patients not doing well on drug therapy are as follows:
  - a. Patients failing to take the medication as prescribed – called “non-adherence”:
    - i. Missed days (drug holidays) – recurring disease symptoms or sudden drug-related side effects, if drug rebound effect, after resuming medication.
    - ii. Irregular timing, resulting in low concentrations of active drug at some points or too high concentrations of active drug when medication is taken at close intervals (may manifest as side effect problem).
    - iii. Medication dropout – patient takes no drug but does not share this information with his/her physician – unexpected disease progression.
  - b. Patient cannot tolerate medication, even if compliant with prescribed regimen (side effects):
    - i. Sensitivity to the prescribed AAD.
    - ii. Concurrent prescribed medications for other chronic diseases are contraindicated for the particular AAD prescribed.
6. When a subject complains to his/her Investigator about the medication and requests a cross-over to receive ablation, the Investigator will have little idea of the root cause of the subject's medication-related problem.

A cross-over management algorithmh could be used to help sort out disease progression issues from drug-related problems.

7. The following guidelines should be addressed by each investigator, prior to making a decision on a subject:

REASON TO INDUCE CROSS-OVER	REASON TO AVOID CROSS-OVER

 
1. Severe symptoms of AF in the absence of evidence that the subject was not taking the prescribed medication and consensus that further medication would be unsuccessful.
 
2. Severe side effects or AF symptoms, evidence of adherence to the prescribed AAD regimen, and no other drug options to which to switch the subject.
 
	
 
1. Evidence that the subject did not take the medications as prescribed and/or took concurrent incompatible medications for other chronic diseases – this subject should undergo Medication Managementi and then return to the hospital 3 weeks later for re-evaluation.
 
2. Evidence not sufficiently strong to merit cross-over, in the minds of the Investigator..
 

h A copy of this algorithm will be available to investigators in this trial as a reference guide to managing subjects with difficulties with their prescribed AAD.

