Safety Population: The Safety Population will include all subjects who have undergone insertion of an ablation catheter, either as Test Group or cross-over subjects; and, subjects who started an investigator-prescribed AAD in the Control Group and did not initiate ablation therapy. Analysis of catheter-related complications will be limited to include only subjects who initiated ablation treatment (catheter insertion) either as Test Group and cross-over subjects.

Adverse drug reactions will be analyzed overall for all the subjects who have taken investigator-prescribed AAD and analyzed separately for cross-over subjects, those in the Test and Control Groups (excluding cross-over subjects).

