8. GENERAL ISSUES FOR STATISTICAL ANALYSIS

8.1 General Statistical Methodology

Descriptive summaries will be provided where appropriate for each of the primary and secondary variables. Tables in the ITT population will summarize data by randomized treatment, tables in the PP and Safety populations will summarize data by treatment actually received if not otherwise specified.

Primary and secondary effectiveness analysis will be conducted in the ITT and the PP populations. All safety data analyses will be performed in the Safety Population.

Health economic and QoL tables will be completed for the ITT population unless otherwise specified. According to the protocol it was planned to use the PP population for health economic and QoL tables, but this was changed to ITT population to perform the analysis based on the randomized treatment groups.

Continuous, quantitative, variable summaries will include the number of subjects (N) with non-missing values, mean, standard deviation (SD), median, minimum, maximum, and quartiles, unless otherwise specified.

Categorical, qualitative, variable summaries will include the frequency and percentage (where applicable) of subjects who are in the particular category. In general, the denominator for the percentage calculation will be based upon the total number of subjects in the study population for the treatment groups unless otherwise specified.

The baseline value will be defined as value entered to the screening/baseline page of the eCRF (terminology screening/baseline is not used consistently in eCRF, but there is only one screening/baseline assessment planned according to protocol).

All analyses will be performed using SAS[®] Software version 9.1.3 or later. ADDPLAN[®] version 5.0.2 or later and East version 5.3 or later may also be used.

For re-calculating of operating characteristics for the analyses of the primary endpoint, the software WinLD will be used.

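### The Control column of the adverse drug reaction tables leaves out cross-over subjects, and side effects are one stated reason to cross over, so its percentage is not the risk of the randomized drug strategy

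*SAP*

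**What the plan says.** SAP 2.2.2 names drug-related adverse events as one of two key safety endpoints. SAP 11.5 summarizes subjects with an event at least possibly related to an antiarrhythmic drug (AAD) "according to Test Group, cross-over group and Control Group (without cross-over subjects". Protocol 13.13 has the same split: "according to Test Group; cross-over; and, Control Group excluding cross-over patients".

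SAP 7 adds a pooled figure: "Adverse drug reactions will be analyzed overall for all the subjects who have taken investigator-prescribed AAD". That figure includes Test subjects, so it is not a Control rate. By default, "tables in the PP and Safety populations will summarize data by treatment actually received if not otherwise specified". Test subjects enter the Safety Population through catheter insertion: "The Safety Population will include all subjects who have undergone insertion of an ablation catheter". No ADR column is planned for all Control subjects as randomized, and none divides the cross-over group's reactions at the ablation date.

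Appendix B, item 7, gives as a reason to induce cross-over: "Severe side effects or AF symptoms, evidence of adherence to the prescribed AAD regimen, and no other drug options". Item 4 argues, on stated assumptions, that patients with severe AAD side effects may be among those most likely to seek cross-over, "resulting in a relatively younger, healthier, and more compliant group of subjects remaining in the drug group".

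**The concern.** A subject stays in the Control column only by not crossing over. Crossing over happens after randomization and can be prompted by the kind of event the table counts. When that happens, the subject and the reaction both move to the cross-over column. The Test column has no matching exclusion.

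Protocol 8.2 says the two groups will be compared on effectiveness and safety endpoints, so the Test and Control percentages will be set side by side. A reader who takes the Control percentage as the ADR risk of a drug-therapy strategy would be reading the risk in a selected part of that arm.

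**Working it through.** **Inputs**
- Cross-over c = 0.50, the planning value in Protocol 13.4 and SAP 6. It is used consistently there: 0.5 × 25% + 0.5 × 5% = 15%, which gives the 0.85 in the sample-size formula.
- True ADR risk in all Controls, p. The documents state none. Assumed 20%, with 10% and 30% as a range.
- r, how many times as likely a subject with an ADR is to cross over as one without. Not stated; assumed 1 to 1.9.

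**Step 1: selection alone**

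Cross-over probability without an ADR: a = c / (p·r + 1 − p). With an ADR: q = r·a. Control column = p(1 − q)/(1 − c). Cross-over column = p·q/c.

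For p = 0.20, c = 0.50, r = 1.5: a = 0.5/1.1 = 0.4545 and q = 0.6818. The Control column is 0.20 × 0.3182/0.5 = 12.7% and the cross-over column is 0.20 × 0.6818/0.5 = 27.3%. Weighted by one half each, they return 20.0%.

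| r | q | Control column | Cross-over column | Combined | Control column if c = 0.20 |
|---|---|---|---|---|---|
| 1 | 0.50 | 20.0% | 20.0% | 20.0% | 20.0% |
| 1.25 | 0.60 | 16.2% | 23.8% | 20.0% | 19.0% |
| 1.5 | 0.68 | 12.7% | 27.3% | 20.0% | 18.2% |
| 1.9 | 0.81 | 7.8% | 32.2% | 20.0% | 16.9% |

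The 20% cross-over in the last column is also an assumption. At c = 0.50 and r = 1.25, 1.5 and 1.9, a true 10% would show as 7.8%, 5.7% and 2.6%, and a true 30% as 25.1%, 20.9% and 15.1%.

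In subjects, if all 161 planned Controls take an AAD, 20% is 32.2 with an ADR. At r = 1.5, 32.2 × 0.682 = 22.0 sit in the cross-over column and 10.2 remain among 80.5 in Control.

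**Step 2: exposure time**

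Step 1 ignores time on drug. Assume constant rates, AAD stopped at ablation, a 20% three-year ADR risk on drug (λ = −ln 0.8/3 = 0.0744), 50% background cross-over (μ = ln 2/3 = 0.2310), and a fraction θ of ADRs that trigger cross-over at once.

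- ADR risk while on drug in all Controls: λ/(λ + μ) × (1 − 0.8 × 0.5) = 0.2435 × 0.6 = 14.6%, whatever θ is.
- Control column: 0.2(1 − θ)/(1 − 0.2θ), which is 20.0% at θ = 0, 14.9% at θ = 0.3 and 9.1% at θ = 0.6.

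The two are equal at θ = (0.2 − 0.1461)/(0.2 − 0.2 × 0.1461) ≈ 0.32. Below that the Control column is too high; above it, too low. If AAD continues after ablation, the all-Control figure is 20.0% and the Control column is lower for any θ above zero.

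**Step 3: what the planned columns can recover**

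The cross-over and Control groups do not overlap, so adding their counts and denominators gives an all-Control figure for ADRs at any time. It does not give ADRs before ablation, because the cross-over column mixes the two periods.

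**The case against.** The strongest reply is that this is a matter of presentation. Protocol 13.16 gives the method for the safety endpoint as descriptive statistics, and no test between arms is planned. The Control column is labelled as excluding cross-overs, the cross-over group has its own column, and table 14.3.7.3 lists the cases. No event is lost. All of this stands, and it limits the weight of the point.

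The link between ADRs and cross-over is also narrower than it first looks. Appendix B requires severe effects or AF symptoms, with adherence and no other drug option, whereas SAP 11.5 counts any event at least possibly related. Protocol 11.4.2 lets Control subjects change drug and stay. Appendix B treats non-adherence and incompatible medication as reasons to avoid cross-over. Its item 4 is conditional, and item 2 intends cross-over well below published rates. Large values of r are therefore upper-range scenarios.

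A reader might infer three stronger things that the documents do not support:
- That every Test subject is counted. The Safety Population takes Test subjects with a catheter inserted, and SAP 7 refers to those who took an AAD.
- That the Control column is conditioned on tolerating the drug. It is conditioned on not crossing over. Some subjects with an ADR switch drug and stay, others leave for AF symptoms, and SAP 7 does not count ablation after the primary endpoint as cross-over.
- That the Control rate is certainly biased low. Step 2 shows that longer exposure can push it the other way.

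The reply does not remove two gaps: no as-randomized Control column is planned, and the pre-ablation rate cannot be rebuilt from the planned columns.

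**Conclusion.** The point holds as a cheap improvement to a descriptive safety summary. The Control percentage in SAP 11.5 is not the ADR risk of the randomized drug strategy, because membership of the column depends on a post-randomization event for which severe side effects are a stated reason.

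The likely direction is too low, as Appendix B's own argument suggests, but this is not established. On an assumed true 20% and the planned 50% cross-over, selection alone gives about 16%, 13% or 8% for r of 1.25, 1.5 or 1.9, and no distortion at r = 1. At 20% cross-over the range is 16.9% to 20.0%. If AAD stops at ablation and fewer than about 30% of ADRs trigger cross-over, the column overstates the all-Control rate. These sizes rest on assumed ADR rates and assumed selection; the only input from the plan is the 50%. It would go too far to say that the safety endpoint cannot compare the arms, since the all-Control count is recoverable by addition.

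**What to change.** In SAP 11.5 and tables 14.3.7.1 and 14.3.7.2:
- Add a Control-as-randomized column beside Test, made up of Control plus cross-over subjects who took an investigator-prescribed AAD.
- Keep the existing three-way split as description.
- Divide the cross-over column into ADRs with onset before and after the first ablation. A subject with reactions in both periods counts in both parts.
- Show AAD exposure time for each column.

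SAP 9.3 already uses this layout for baseline tables: groups as randomized, plus AAD-only and cross-over subgroups within Control. SAP 11.3 already places serious catheter-related events by time since ablation, so event and ablation dates can be linked. No new data collection appears necessary.

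The cost is a little more programming. The exposure figure is the larger part, because it must be derived from medication records whose start and end dates SAP 9.4 expects may be incomplete. The comparison stays descriptive: Test and Control are both still limited to subjects who received certain treatments after randomization.
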